3.3.3 Population Register

To ascertain a correct population at risk time in the data analysis, information on dates of emigration and death for all patients will be retrieved from the Register of Population at Statistics Sweden.

3.3.4 Socioeconomic factors

Data on socioeconomic factors will be obtained from various national registers available in the LISA database maintained by SCB. In LISA information is available for all people, aged 16 or older, who have been a resident in Sweden by the end of the year. Data is available at least from 1990.

4. SUBJECT POPULATION

The patient population will consist of all patients who have been hospitalised in Sweden at least once since 1987 with a diagnosis during hospitalisation of BD. Patients with a later diagnosis of schizophrenia spectrum disorder will be excluded.

4.1 Inclusion criteria

1. Patients with a diagnosis of BD, see Appendix B Table 1 for the ICD10 and ICD9 diagnosis.

4.2 Exclusion criteria

1. Patients with a diagnosis of any schizophrenia spectrum disorder after the diagnosis of bipolar disorder, see Appendix B, Table 2 for the ICD10 and ICD9 diagnosis.

5. STUDY VARIABLES

5.1 Study variables from different registers

Data on patients with a diagnosis of BD and/or schizophrenia spectrum disorder who have been hospitalized due to this disease (the latest diagnose will be valid for inclusion) at any time since 1987 will be extracted from following registers.

5.1.1 National Patient Register

- Date of admission and length of stay
- Main diagnosis
- Secondary diagnosis
- DRG codes set by the discharge hospital

5.1.2 Prescription Drug Register (see attachment 1)

- Dispatching pharmacy (council code for the dispatching pharmacy)
- Dispensed prescribed medications
- Patients information (Personal code number, age and gender, place for national registration)
- Prescriber information (occupation, education code, specialist code)
- Place of work information (County, working place code, ownership, health care, activity direction)
- Prescription information (Prescription date, type of ordination, type of benefit, category of execution, start package, permitted exchange, exchange code, prescribed identity of goods (connected to the register of goods with access to ATC-

code, name of prescribed drug, DDD per package etc.), number of prescribed packages, dispatched identity of goods, type of goods, number of complete packages, dosage instruction)

• Cost (price each, total cost, patient cost, county cost, VAT, surplus cost)

5.1.3 Population Register

- Dates of emigration
- Date of death

5.1.4 Socioeconomic Data

- Educational level
- Marital status
- Living situation
- Occupation status
- Sick leave
- Income level
- Income source (salary/sick pension)
- Country of birth

5.2 Other variables

co-morbidities of special interest at index visit, before treatment with quetiapine XR and/or quetiapine IR and co-medications of special interest at the index visit and afterwards.

5.2.1 Co-morbidities

- Ischemic heart disease
 - ICD-9: 413
 - ICD-10: I 20.9, I 25.1
- Peripheral arterial disease including extra cerebral, non-coronary arterial thromboembolism
 - ICD-9: 440,441,444
 - ICD-10: I70- I79
- Chronic obstructive pulmonary disease (COPD)

- ICD-9: 496
- ICD-10: J44.9
- Psychiatric admission history including number of previous admissions.
 All F psychiatric (diagnosis) will be collected, with special interest of diagnoses
 specified see Table 3-4. All V, X and Y diagnosis (External causes of morbidity and mortality) are included, see appendix B, Translator ICD10 to ICD9.
- Drug and alcohol abuse
 - ICD-9; 305.0, 291.89, 292, 305.00-305.93, 304.00-304.93
 - ICD-10: F10-F19
- Cancer
 - ICD-9: 140-209
 - ICD-10: C00-C99
- Endocrine disease
 - ICD-9: 240-246
 - ICD-10: E16-E99
- Diabetes mellitus
 - ICD-9: 250
 - ICD-10: E10-E11
- Neurological
 - ICD-9.: 320-389
 - ICD-10: G00-G99 (excluding G45)
- Heart failure
 - ICD-9: 428
 - ICD-10: I 50
- Myocardial Infarction
 - ICD-9. 410, 429
 - ICD-10: I 21-22

- Stroke and TIA
 - ICD-9: 430-438
 - ICD-10: I 60-69
- Hypertension
 - ICD-9: 401
 - ICD-10: I 10
- Renal failure
 - ICD-9: 586, 403, 404, 639.3
 - ICD-10: N 17-19
- Intoxication
 - ICD9: 960-979
 - ICD10: T4n

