2.2 Secondary objectives

- 1. To describe co-morbidity, demographics, sick leave, early retirement and socioeconomic factors in patients with BD and on treatment with quetiapine XR and/or quetiapine IR before and at the index date.
- 2. To describe the detailed clinical treatment (including duration of treatment, doses, drug switches, and add-on therapy) in patients with BD, including all drug treatment after the index date.
- 3. To describe co-morbidity, demographics, sick leave, early retirement and socioeconomic factors in patients with BD, including all drug treatment before and at the index date

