9. STATISTICAL METHODS AND SAMPLE SIZE DETERMINATION

9.1 Statistical evaluation – general aspects

A DBA is a study in which epidemiological methods including other methods that can be used to analyse human population health data.

The principal features of the planned statistical evaluation will involve descriptive statistics analysis the different populations.

The descriptive analysis (both for the primary and secondary objectives) will for the continuous variables be done by calculating mean, standard deviation, 95% CI, number of observations, minimum, maximum, median and number of missing observation and for categorical variables number of observations, frequencies and percentage.

Data base Audit Study Protocol DBA Code VD-NS-1101 Edition Number 1.0 Date

The analysed variables at the index date will be age, gender, educational level, marital status, living situation, occupation status, sick leave, income level, income source (salary/sick pension), country of birth, co-morbidities (as specified in section 5), co-medications (as specified in section 5).

The prescribers occupation, education and specialist code will be analysed, ownership (private/public) and country divided in quetiapine IR and quetiapine XR.

The variables analysed before the index date will be; number of hospital stays and sum of length of hospital stays.

The treatments after the index date will be analysed for the following variables: duration, dosage, drugs switches, DDD per package, number of prescribed packages for quetiapine IR/XR and co-medications including dosage and duration of these co-medications.

Attempts will be made to find the prescribed dose and the diagnosis from the free text on the prescription label on the drug for quetiapine IR and quetiapine XR either by text mining or by manually go through the different prescription labels.

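### The ICD-10 co-morbidity lists in Protocol section 5.2.1 leave TIA (G45), thyroid disease (E00-E07) and diabetes codes E12-E14 in no category, and several ICD-9/ICD-10 pairs do not define the same condition

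*Protocol*

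**What the plan says.** Section 5.2.1 of the Protocol gives an ICD-9 and an ICD-10 list for each co-morbidity of interest. On the points that matter here:

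- Neurological: ICD-9 320-389; ICD-10 "G00-G99 (excluding G45" being the one stated exception.
- "Stroke and TIA": ICD-9 430-438; ICD-10 I60-I69.
- Endocrine disease: ICD-9 240-246; ICD-10 E16-E99.
- Diabetes mellitus: ICD-9 250; ICD-10 E10-E11.
- Renal failure: "ICD-9: 586, 403, 404, 639.3" against ICD-10 N17-N19.

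Section 9.1 ties the analysis to these lists: the index-date variables include "co-morbidities (as specified in section 5". The tables serve section 2.2, where secondary objective 1 is "To describe co-morbidity, demographics, sick leave, early retirement and socioeconomic factors in patients with BD and on treatment with quetiapine XR and/or quetiapine IR" and objective 3 asks for the same in all patients with bipolar disorder. Section 5.1.1 extracts the main diagnosis and "Secondary diagnosis" from the National Patient Register.

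**The concern.** The study is descriptive, so the co-morbidity tables are themselves a result, and no later model corrects a row that was defined wrongly. The protocol does not leave the code lists open for later specification. It fixes them, and an analyst who follows the text will produce rows that do not hold what their labels say.

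The clearest case can be seen from the lists alone. G45 is taken out of one category, and the only visible reason is that another category names TIA. That other category does not receive it. The endocrine and diabetes lists raise a related problem: the same label covers different diseases depending on which ICD version the record was coded in. Lithium, insulin, metformin and sulfonylurea are all tabulated under section 5.2.2. A reader of the report could therefore set an endocrine row lacking most ICD-10 thyroid disease beside lithium use, or see patients on antidiabetic drugs with no diabetes recorded.

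**Working it through.** There is no planned figure to reproduce. The check is set arithmetic on the listed ranges, followed by a pair-by-pair comparison.

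**Step 1: coverage of ICD-10 chapters E and G.** Inputs are all the ICD-10 lists in section 5.2.1, expanded to three-character codes, with T4n read as T40-T49.

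- Chapter G: 100 slots (G00-G99) minus G45 leaves 99 covered. G45 is not in I60-I69 or any other list. Uncovered: 1 code, G45.
- Chapter E: covered codes are E10-E11 (2) and E16-E99 (84), together 86. Uncovered: 100 - 86 = 14 slots, namely E00-E09 (10) and E12-E15 (4).
- No three-character ICD-10 code falls in two categories.

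Some of the 14 slots may be empty, since E08-E09 may not be in use in the version applied. The substantive losses are E00-E07 (8 codes) and E12-E14 (3 codes).

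**Step 2: do the two halves of each pair define the same condition?** This step needs the standard meaning of the codes, which the protocol does not reproduce.

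| Category | ICD-9 list | ICD-10 list | Mismatch |
|---|---|---|---|
| Stroke and TIA | 430-438 (includes 435, TIA) | I60-I69 | TIA present in ICD-9, absent in ICD-10 |
| Endocrine | 240-246 (thyroid) | E16-E99 | Lists lie on opposite sides of diabetes and describe largely different diseases |
| Diabetes | 250, whole category | E10-E11 | E12-E14 dropped |
| Neurological | 320-389 | G00-G99 without G45 | ICD-9 360-389 are eye and ear codes |
| Myocardial infarction | 410, 429 | I21-I22 | 429 is broader than infarction |
| Renal failure | 586, 403, 404, 639.3 | N17-N19 | 584 and 585 (acute and chronic failure) absent in ICD-9; 403 and 404 have no counterpart in the ICD-10 list |
| Drug and alcohol abuse | 303 not listed | F10-F19 | Alcohol dependence missing in ICD-9 |
| Intoxication | 960-979 | T4n | Full drug-poisoning range (T36-T50) not covered in ICD-10 |

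The first three rows carry the point. The endocrine mismatch is visible even without code meanings: the protocol places diabetes at 250 and at E10-E11, and its endocrine block comes before diabetes in one version and after it in the other.

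**Step 3: direction and size.** For a condition with coded prevalence p among N patients, the undercount in its row is N x p x (1 - q), where q is the share already flagged through another code in the same row. The protocol gives neither p nor q, so only the direction follows: too few for TIA, thyroid disease and E12-E14 diabetes in ICD-10 records. In ICD-9 records, codes 429 and 360-389 push the other way, towards too many.

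**The case against.** Several things can fairly be said for the plan.

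- **Raw diagnoses are kept.** Section 5.1.1 extracts main and secondary diagnoses without limiting them to these lists. Nothing is lost at extraction, and regrouping can be done at analysis. This stands, and it means the correction need not precede the data request.
- **Only secondary description is touched.** The primary objective is treatment pattern, and section 1.2 rules out outcome analysis between the formulations. This also stands.
- **Appendix B may help.** It is not shown. Its ICD-10 to ICD-9 translator is cited in section 5.2.1 only under the psychiatric and external-cause item, so it does not visibly repair the somatic lists. It could bear on the abuse codes, so the missing 303 is a query rather than an established error.
- **The ICD-9 side may matter little.** Index dates start on 1 January 2009, and section 3.1 mentions data from six months before first dispensing. If co-morbidity uses a short look-back, presumably few ICD-9 records enter. That weakens the concern about ICD-9 codes such as 429 and 360-389, but not the ICD-10 gaps, which then apply to most records.

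A reader might infer more than the documents support:

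- That the stroke and TIA row holds no TIA, or the endocrine row no thyroid disease, at all. Both ICD-9 lists include them, and a residual ICD-10 code such as E89 (postprocedural hypothyroidism) lies inside E16-E99. For the same reason it is too strong to say that the two endocrine lists share no disease.
- That the COPD pair is also mismatched. ICD-9 496 and J44.9 are narrow but consistent, and widening only the ICD-10 side would create a mismatch.
- That 429 should simply be deleted. It includes sequelae of infarction, so its inclusion may be deliberate.
- That a headcount can be given. An assumed thyroid prevalence of 5-15% in the planned 14 000-16 000 patients gives 0.05 x 14 000 = 700 to 0.15 x 16 000 = 2 400. The prevalence has no basis in the protocol, and the sum sets q = 0, so for that assumed prevalence it is a ceiling and not an estimate.

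**Conclusion.** The point holds for the ICD-10 lists. As written, section 5.2.1 places G45, E00-E07 and E12-E14 in no category, and section 9.1 carries those lists into the tables for secondary objectives 1 and 3. ICD-10-coded TIA, thyroid disease and E12-E14 diabetes will be undercounted there, and the endocrine row will mean largely different things in ICD-9 and ICD-10 records. The size cannot be computed from the protocol.

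The coverage gaps rest on the protocol's own ranges alone. Naming the diseases affected, and judging the other pairs, rests on the standard ICD code meanings and on the unseen Appendix B not already correcting the lists. The primary objective, the inclusion of patients and the extraction of data are not affected. The lists should be corrected before the tables are run.

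**What to change.** Edit section 5.2.1 before analysis:

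1. Add G45 to the ICD-10 list for stroke and TIA.
2. Extend the ICD-10 list for diabetes to E10-E14.
3. Make the endocrine category cover the same diseases in both versions. Either add E00-E07 to the ICD-10 list and the matching non-thyroid codes to the ICD-9 list, or rename the row Thyroid with 240-246 and E00-E07. In either case say where E15 and E89 belong.
4. Reconcile the remaining unequal pairs so that each ICD-9 and ICD-10 list defines one condition: neurological (ICD-9 320-389), myocardial infarction (429), renal failure (584 and 585 absent; 403 and 404 unmatched), abuse (303 absent) and intoxication (T4n against 960-979). Check them against the Appendix B translator. If COPD is widened, widen both sides together.

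The cost is a small amount of recoding work. It needs no further patients and, since main and secondary diagnoses are already extracted, no further data.

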5.2.2 Co-medications

- Anti-depressant: N06A;
 - N06AA, N06AB, N06AC, N06AD, N06AE, N06AF, N06AG, N06AX
- Benzodiazepine-derivates: N05BA;
 - NO5BA01, NO5BA02, NO5BA03, NO5BA04, NO5BA05, NO5BA06,
 - NO5BA07, NO5BA08, NO5BA09, NO5BA10, NO5BA11, NO5BA12,
 - NO5BA13, NO5BA14, NO5BA15, NO5BA16, NO5BA17, NO5BA18, NO5BA22
- Narcoleptics: N05A;
 - N05AA, N05AB, N05AC, N05AD, N05AE, N05AF, N05AG, N05AH, N05AK,
 - N05AL, N05AN, N05AX
- Quetiapine IR: N05AH04
- Quetiapine XR: N05AH04
- Anti-epileptics: N03A;
 - N03AA, N03AB, N03AC, N03AD, N03AE, N03AF, N03AG
 - NO3AG01, NO3AG02, NO3AG03, NO3AG04, NO3AG06
 - NO3AX

Valproate: N03AG01

• Sulfonylurea: A10BB

• Metformin: A10Ba

• Insulin: A10A

Broncho dilatating drugs: R03

• Betablockers: C07

• ARB: C09C, C09D

• ACE: C09A, C09B

• Ca-antagonists: C08C, C08D

• Thiazides: C03A

• Loop diuretics: C03C

• Statins: C10AA

• Lamotrigine: N03AX09

• Lithium: N05AN01

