2. DBA OBJECTIVES

2.1 Primary objective

The primary objective of the study is to describe the detailed clinical treatment (including duration of treatment, doses, drug switches, and add-on therapy), in patients with BD and on treatment with quetiapine XR and/or quetiapine IR before, at and after the index date.

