3.1 Study Design

This is an epidemiological registry study on all patients who have been hospitalised in Sweden at least once since 1987 with a diagnosis during hospitalisation of BD and/or schizophrenia spectrum disorder. Index visit (baseline) is defined as the date when a patient dispensed their first prescription of quetiapine XR and/or quetiapine IR. Patients with index visit between 1st of January 2009 and 31st of December 2010 will be more detailed described, and data will be collected six months prior to the first dispensed prescription of quetiapine XR and/or quetiapine IR. Patients started their treatment with quetiapine XR and/or quetiapine IR before 1st of January 2009 will have 1st of January 2009 as index visit.

May 2008 quetiapine XR was launched for the indications schizophrenia and bipolar mania in Sweden and March 2009 quetiapine XR and IR was launched in bipolar depression.

Data on patients with schizophrenia spectrum disorder will be collected in order to allow us to exclude patients who have been re-diagnosed to or from bipolar disorder. The latest diagnose is defined as the patients diagnose, i.e. if a patient gets a schizophrenia spectrum disorder diagnose after diagnose of bipolar disorder, the patient will not be included in the study.

Figure 1 Patient flow

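### By the protocol's own codes, the neuroleptic co-medication class contains quetiapine and lithium, so it cannot describe antipsychotic add-on therapy in the quetiapine cohort

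*Protocol*

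**What the plan says.** Section 5.2.2 of the protocol lists the co-medications of interest by ATC code. One class is headed "Narcoleptics: N05A". The label appears to mean neuroleptics, since the subgroup that holds quetiapine is part of it. Its subgroups are given as "N05AA, N05AB, N05AC, N05AD, N05AE, N05AF, N05AG, N05AH, N05AK" followed by "N05AL, N05AN, N05AX". No code is excluded.

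The same list has separate lines for "Quetiapine IR: N05AH04", "Quetiapine XR: N05AH04" and "Lithium: N05AN01".

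Four other places give the class its role:

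- Section 2.1 makes the description of treatment, "including duration of treatment, doses, drug switches, and add-on therapy", the primary objective in patients on quetiapine XR and/or IR.
- Section 3.1 sets cohort entry: "Index visit (baseline) is defined as the date when a patient dispensed their first prescription of quetiapine XR and/or quetiapine IR". Patients who started before 1 January 2009 take that date as index instead.
- Section 5.2 has co-medications assessed at index and after it.
- Section 9.1 refers the index-date co-medication analysis to the Section 5 list. After index it again analyses co-medications, with their dosage and duration.

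**The concern.** In the quetiapine cohort, a co-medication class should show which other drugs a patient takes besides quetiapine. This class includes the drug that brings the patient into the cohort, so it is met by quetiapine alone. A patient on quetiapine only and a patient on quetiapine plus a second antipsychotic get the same flag.

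Add-on therapy is named in the primary objective. Section 1.2 also explains why it is of interest: XR is thought to serve mainly as the foundation treatment, and IR more often as a lower-dose addition to other drugs. A class that takes the same value for XR and IR users cannot show whether their use of other antipsychotics differs. Dosage and duration summaries for the class after index would also mix quetiapine with the other drugs.

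Lithium raises a second, separate problem. Its code falls in the same class, so quetiapine plus lithium is counted as quetiapine plus a neuroleptic. Removing quetiapine does not cure this.

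**Working it through.** The plan gives no figure to reproduce. The check is a code match, followed by an illustration of size.

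**Code match (all codes from Section 5.2.2)**

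| Drug | Code | Subgroup it falls in | Class |
|---|---|---|---|
| Quetiapine IR | N05AH04 | N05AH | Neuroleptic |
| Quetiapine XR | N05AH04 | N05AH | Neuroleptic |
| Lithium | N05AN01 | N05AN | Neuroleptic |
| Valproate | N03AG01 | N03AG | Anti-epileptic |
| Lamotrigine | N03AX09 | N03AX | Anti-epileptic |

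The last two rows show that the list nests single drugs under parent classes as a matter of style.

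**Is an exclusion implied?** Section 5.2.1 writes one out where it is wanted: the neurological co-morbidity class covers the ICD-10 G codes except G45. Nothing similar is written for N05A.

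**Size.** Let *a* be the share of the quetiapine cohort truly on another antipsychotic and *l* the share on lithium. The documents give neither, so both are assumptions, taken as independent. Among patients with a quetiapine dispensing in the window, the share flagged is:

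- list as written: 100%, for any *a* and *l*
- quetiapine removed, lithium kept: 1 − (1 − *a*)(1 − *l*)
- quetiapine and lithium both removed: *a*

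For example, with *a* = 0.10 and *l* = 0.30, the middle line gives 1 − 0.90 × 0.70 = 0.37.

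| *a* | As written | Quetiapine removed, *l* = 10% | *l* = 30% | *l* = 50% | Both removed |
|---|---|---|---|---|---|
| 10% | 100% | 19% | 37% | 55% | 10% |
| 30% | 100% | 37% | 51% | 65% | 30% |
| 50% | 100% | 55% | 65% | 75% | 50% |

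The inflation due to lithium alone is 1 − (1 − *a*)(1 − *l*) − *a* = *l*(1 − *a*). It reaches *l* itself only if no lithium user takes another antipsychotic. With *a* = 30% and *l* between 20% and 40%, it is 0.20 × 0.70 = 14 points to 0.40 × 0.70 = 28 points.

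**The case against.** The strongest reply is that the list is a nested set of drugs of interest, not a set of exclusive categories. Valproate and lamotrigine also sit inside a listed parent class. Quetiapine and lithium have their own lines, and Section 9.1 names quetiapine separately from co-medications after index. The ordinary sense of co-medication excludes the study drug. Section 5.1.2 collects every dispensed product with its code and name, so the classes can be rebuilt at any time. The derivation of add-on therapy may also be set out in a statistical analysis plan that is not shown.

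Part of this stands. Nesting and double listing are not errors in themselves, and no information is lost. An analyst who sees the problem can avoid it. The reply does not rescue the rule as stated, because the protocol fixes the code list and Section 9.1 points to it. Nothing says that the separate lines are taken out of the class. Different analysts could remove quetiapine, both drugs or neither, and the table above shows how far the results would differ. The nesting of valproate and lamotrigine is harmless because neither drug defines cohort entry and both sit under a fitting label.

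A reader might infer more than the documents support:

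- **That all patients are flagged at index.** Patients given 1 January 2009 as index need not have a dispensing that day. They are flagged once one falls in the window.
- **That lithium inflates the rate by a known amount.** No lithium share is given, and any figure rests on an assumed one.
- **That a study hypothesis is defeated.** Section 1.2 reports the XR and IR contrast as a belief and calls the assessment explorative.
- **That quetiapine should leave the class everywhere.** Secondary objectives 2 and 3 in Section 2.2 cover bipolar patients on any drug treatment. There, quetiapine properly counts as one of the antipsychotics.

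**Conclusion.** The point holds for the quetiapine cohort. By the protocol's own codes, the neuroleptic class includes the study drug, and no exclusion is stated. Applied as written, the class proportion is 100% among patients with a quetiapine dispensing in the assessment window and says nothing about antipsychotic add-on therapy. This follows from the definitions and needs no assumption about drug use.

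The lithium problem holds in both populations. Its size is unknown, and the percentages shown rest on assumed shares and independence. This is a wrong definition in a stated list, not a missing detail. It affects one descriptor within the primary objective and leaves the cohort, the data request and the other drug classes unchanged.

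**What to change.** Amend Section 5.2.2, and refer to the amended classes in Section 9.1:

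- **Quetiapine cohort (Sections 2.1 and 2.2, objective 1):** for co-medication and add-on therapy, use a class of other antipsychotics, defined as N05A excluding N05AH04 and N05AN.
- **Concurrent XR and IR use:** describe it through the existing quetiapine lines, not as a neuroleptic co-medication. The two formulations share one ATC code, so they must be told apart by the product identity and drug name collected under Section 5.1.2.
- **All-treatment bipolar population (Section 2.2, objectives 2 and 3):** keep quetiapine in the antipsychotic class and exclude N05AN.
- **Lithium:** report it on its own existing line in both populations.
- **Label:** correct the class name so that it matches the codes.

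The cost is a short text change and the matching lines of the analysis program. The register extract already holds the codes and product names, so no new data are needed.
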